## 7 INVESTIGATIONAL PLAN

### 7.1 Study Design

ADU-CL-20 is an open-label, multicenter Phase 2 clinical trial to evaluate the efficacy and safety of intratumoral ADU-S100 (also referred to as MIW815) administered with standard of care treatment (i.e. pembrolizumab) in the first-line setting. The population will consist of adults with PD-L1 positive recurrent or metastatic HNSCC. Up to twenty (20) evaluable subjects will initially be enrolled.

The trial design consists of a Screening Period, Treatment Period, and an End of Treatment (EOT) visit as depicted in Figure 7-1. All eligible subjects will receive intravenous (IV) infusions of pembrolizumab (200 mg; per approved product label) and intratumoral injections of ADU-S100 (800 mcg/lesion). During the Treatment Period, study medications will be administered in 21-day dosing cycles; tumor responses will be evaluated at 9-week intervals. If the injected lesion(s) shows signs of significant regression (i.e. shrinkage) such that repeat administration of ADU-S100 is no longer possible in any lesion, the subject will be scheduled to complete the EOT visit and may continue treatment with pembrolizumab as monotherapy/standard of care outside the context of the ADU-CL-20 clinical trial. Subjects who do not complete at least one response evaluation, unless they discontinued due to toxicity, will not be considered evaluable. An EOT visit will be conducted to assess subsequent anti-cancer therapy, and complete safety reporting requirements. A schedule of visits and procedures is provided in [Table 2-1](#).

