### **8.3 Subject Completion, Treatment Discontinuation, or Removal from Study**

#### **8.3.1 Subject Completion**

Subject completion is defined as completion of scheduled visits and assessments up to and including the last protocol-specified visit; or when the subject has experienced a clinical endpoint (e.g. death, unacceptable toxicity, confirmed disease progression) that precludes further continuation in the study.

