#### **8.3.2 Discontinuation from Study Treatment**

A subject should be discontinued from treatment for any of the following reasons:

- Withdrawal of consent or subject requests study treatment discontinuation for any reason
- Occurrence of any medical condition or circumstance that exposes the subject to substantial risk and/or does not allow the subject to adhere to the requirements of the protocol
- Confirmed disease progression ([Section 10.2.1.1](#))

- Any unacceptable toxicity, SAE, clinically significant AEs, severe laboratory abnormality, intercurrent illness, or other medical condition which indicates to the Investigator that continued participation is not in the best interest of the subject
- Subject experiences any Grade 4 adverse event, with the exception of those listed in [Table 9-2](#)
- Pregnancy
- Subject failure to comply with protocol requirements or study-related procedures. [Dosing compliance issues should be reviewed on a case-by-case basis with Medical Monitor.]
- Termination of the study by the Sponsor or regulatory authority

Subjects who experience unacceptable toxicity directly attributable to pembrolizumab may continue on study and receive ADU-S100 as single agent study treatment with approval by the Medical Monitor.

If a subject's study treatment (ADU-S100 and/or pembrolizumab) is discontinued, this will not result in automatic withdrawal of the subject from the study. The Investigator will provide a reason for treatment discontinuation. Subjects who discontinue treatment will be encouraged to complete EOT and follow-up assessments.

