### **8.3.3 Subject Discontinuation/Withdrawal from the Study**

A subject will be withdrawn from the study for any of the following reasons:

- Death
- Lost to follow-up
- Withdrawal of consent
- Termination of the study by the Sponsor or regulatory authority

Subjects who do not complete at least one response evaluation, prior to their withdrawal from the study, unless they discontinued due to toxicity, will not be considered evaluable for the primary efficacy endpoint.

If a subject is lost to follow-up, reasonable efforts must be made by the study site personnel to contact the subject and determine the reason for discontinuation/withdrawal. The measures taken to follow up must be documented.

When a subject withdraws for other reasons before completing the study, the Investigator will provide a reason for withdrawal in the electronic case report form (eCRF).

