### 12.1 Sample Size Determination

The original sample size was based on a Simon's 2-stage minimax design (Simon 1989) test the null hypothesis that the objective response rate (ORR; complete response [CR] and partial response [PR]) per Response Evaluation Criteria in Solid Tumors (RECIST) v1.1) is less than or equal to 0.19 versus the alternative hypothesis that ORR is greater than or equal to 0.38, with a Type 1 error rate of 0.05 and power of 80%.

Because of truncated enrollment, the total sample size will be limited to approximately 20 evaluable subjects as planned for the first stage.

Subjects who do not complete a response assessment will not be considered evaluable.

The ORR criteria are based on the pembrolizumab first in human study in a similar patient population with similar prior treatment where the response rate was approximately 19% (Burtneß et al. 2018; Rischin et al. 2019).

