### 12.3 Analysis Sets

The following analysis sets will be used for this study:

***Evaluable Analysis Set (EAS):*** All subjects who received any amount of study drug and have at least one evaluable response assessment or were discontinued due to toxicity. The

EAS will be used for analysis of the primary efficacy endpoint and clinical activity.

**Safety population**, defined as all subjects who receive any amount of study drug. All safety analyses will be based on this population.

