## 6.2 Determination of Sample Size

The study will include up to 34 evaluable subjects to assess the clinical efficacy of ADU-S100 administered in combination with pembrolizumab in adults with head and neck cancer. Power calculations based on a Simon’s 2-stage minimax design test the null hypothesis that the objective response rate (ORR) is less than or equal to 0.19 versus the

alternative hypothesis that the ORR is greater than or equal to 0.38 with a Type 1 error rate of 0.05 and power of 80%. A sample size of 20 evaluable subjects will be enrolled in the first stage. If the total number responding is greater than or equal to 4, an additional 14 evaluable subjects will be enrolled in the second stage for a total of 34 evaluable subjects. For the second stage, if the total number responding is less than or equal to 10, the effectiveness of treatment based on ORR will be rejected.

If treatment is actually not effective and  $ORR \leq 0.38$ , then the expected sample size is 25.3 evaluable subjects with a 0.456 probability of early termination and a 0.044 probability of incorrectly concluding the treatment is effective (the target for this Type 1 error rate was 0.05 or less). If the treatment is actually effective, there is a 0.200 probability of incorrectly concluding it is not effective (the target for this Type 2 error rate was 0.200 or less).

Subjects who do not complete a response assessment will not be considered evaluable and will be replaced.

The ORR criteria are based on the pembrolizumab first-in-human study in a similar patient population with similar prior treatment where the response rate was approximately 19% (Burtneß et al. 2018; Rischin et al. 2019).

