## 7.2 Analysis Populations

The analysis populations are defined as follows:

- **All Treated Population:** Includes all subjects who received any amount of either study drug.
- **Evaluable Analysis Set (EAS):** Includes all subjects who received any amount of either study drug and additionally who either have at least one evaluable response assessment or who discontinued the study for a reason of toxicity, clinical progression, or death.
- **Modified All Treated Population:** The protocol inclusion criteria require eligible subjects to be PD-L1 positive (defined as combined positive score [CPS]  $\geq 1$ ). If any subject with baseline CPS  $< 1$  were to be enrolled (a protocol deviation), then a Modified All Treated Population is defined as the All Treated Population excluding subjects with baseline CPS  $< 1$ .

Though subjects with baseline CPS  $< 1$  are not expected on study, if this were to occur, the Modified All Treated Population would be used for Efficacy summary analysis, rather than the All Treated Population. Otherwise, the All Treated Population will be used for both Efficacy and Safety analyses. Sensitivity analysis of efficacy on the EAS population will be presented only if there is a considerable difference between the EAS and the All Treated Population.

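### The count of about 20 evaluable subjects and the Evaluable Analysis Set follow different rules for subjects with no response assessment, and SAP 7.2 keys membership to leaving the study rather than stopping treatment

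*SAP*

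**What the plan says.** **Who is evaluable.** SAP 7.2 includes in the EAS treated subjects "who either have at least one evaluable response assessment or who discontinued the study for a reason of toxicity, clinical progression, or death". SAP 7.6 declares this widening of the Protocol's set to deaths and clinical progression, but does not tie it to leaving the study. SAP 6.2, where the evaluable subjects are counted, says: "Subjects who do not complete a response assessment will not be considered evaluable and will be replaced". Protocol 12.1 has the same rule without replacement: "Subjects who do not complete a response assessment will not be considered evaluable". Protocol 12.3 takes a middle course, admitting subjects who "have at least one evaluable response assessment or were discontinued due to toxicity". The toxicity-only exception also appears in Protocol 7.1 ("Subjects who do not complete at least one response evaluation, unless they discontinued due to toxicity, will not be considered evaluable"), the Synopsis, 8.3.3 and 10.2.1.1.

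**Treatment versus study.** Of a subject whose study treatment is stopped, Protocol 8.3.2 says that "this will not result in automatic withdrawal of the subject from the study". Protocol 8.3.3 opens with "A subject will be withdrawn from the study for any of the following reasons" and lists four: death, loss to follow-up, withdrawal of consent, and termination of the study. Protocol 8.3.1 counts a subject as having completed "when the subject has experienced a clinical endpoint (e.g. death, unacceptable toxicity, confirmed disease progression) that precludes further continuation in the study".

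**Use of the set.** SAP 7.4.4 and 7.6 base the primary objective response rate (ORR) on the All Treated Population. SAP 7.4.5 repeats it on the EAS, while SAP 7.2 presents EAS efficacy only if the EAS differs considerably from All Treated.

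**The concern.** A treated subject with no post-baseline tumour assessment cannot be a RECIST responder. Whether that subject is in the denominator therefore moves the response rate in one direction only. The documents classify such a subject differently depending on the section. A subject who dies in week 4 is in the EAS under SAP 7.2 and 7.6, but is non-evaluable and replaced under SAP 6.2.

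SAP 7.2 has a second weakness. SAP 7.3.1 reports the reason for stopping treatment separately from the reason for leaving the study, so a programmer has to choose a field. The wording of 7.2 points to the study field. By Protocol 8.3.3 that field need not ever hold toxicity or clinical progression, and the intent stated in SAP 7.6 would then not be carried out.

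At stake are the EAS response rate, the comparison of the EAS with All Treated that decides whether EAS results are shown under 7.2, and the count toward 20.

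**Working it through.** **1. The plan's own figure.** The documents give no figure for this point. The nearest is the design that produced the count of 20 (SAP 6.2: null 0.19, alternative 0.38, continue at 4 or more of 20, success above 10 of 34). Exact binomial calculation gives early termination 0.4561 and type 1 error 0.0446 at 0.19, and power 0.8001 at 0.38. The SAP prints 0.456, 0.044 and a type 2 error of 0.200. The count of 20 is therefore a count of evaluable subjects, and its meaning depends on that definition.

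**2. The rules side by side**, for a treated subject with no response assessment:

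| Situation | SAP 6.2, Protocol 12.1 | Protocol 7.1, 8.3.3, 10.2.1.1, 12.3 | SAP 7.2, read literally | SAP 7.6 |
|---|---|---|---|---|
| Died | Not evaluable | Not evaluable | In EAS | In EAS |
| Stopped treatment for toxicity | Not evaluable | Evaluable | Out, unless toxicity is recorded as the reason for leaving the study | In EAS |
| Stopped treatment for clinical progression | Not evaluable | Not evaluable | Out, unless recorded as the reason for leaving the study | In EAS |
| Lost or withdrew consent, no such reason | Not evaluable | Not evaluable | Out | Out |

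The difference between the Protocol's toxicity-only rule and SAP 7.6 is a declared change. Two differences are not declared: the first column against the last two, and SAP 7.2 against 7.6. Deaths are safe under 7.2, because death is a listed withdrawal reason; among the SAP rules they are lost only under 6.2.

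**3. How many subjects can be left without an assessment.** The first scheduled scan is Cycle 4 Day 1, which is Day 64 (3 × 21 + 1), with a window of 7 days before. Footnote 5 of the Schedule of Events, in both documents, adds a scan at the end-of-treatment (EOT) visit if more than 6 weeks (42 days) have passed since the last evaluation. EOT is 30 (+7) days after the last dose. The baseline scan falls between Day -28 and Day -1, and there is no Day 0.

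- Last dose Day 22 (Cycle 2 Day 1): EOT on Day 52, at least 52 days after baseline. A scan is always due.
- Last dose Day 8: EOT on Day 38, which is 38 to 65 days after baseline. A scan may or may not be due.
- Last dose Day 1: EOT on Day 31, which is 31 to 58 days after baseline. A scan may or may not be due.

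These use the nominal 30 days. EOT can also come earlier, before new anti-cancer therapy. Protocol 10.2.1.1 asks for prompt imaging on deterioration or suspected progression. The subjects at issue are therefore those who stop in Cycle 1 with a recent baseline scan, who have an early EOT, or who miss or cannot have the scan.

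**4. Size.** With x responders among n treated and e unscanned non-responders excluded, EAS ORR = x / (n − e). Assume n = 20 and x = 5; e is not in the documents and is varied. Intervals are 95% Clopper-Pearson, the method in SAP 7.4.4.

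| e | ORR | 95% CI |
|---|---|---|
| 0 | 5/20 = 25.0% | 8.7 to 49.1 |
| 1 | 5/19 = 26.3% | 9.1 to 51.2 |
| 2 | 5/18 = 27.8% | 9.7 to 53.5 |
| 3 | 5/17 = 29.4% | 10.3 to 56.0 |

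The ratio x / (n − e) cannot fall as e rises. It stays level only when x = 0.

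**The case against.** The best reply is that this is loose wording with little consequence. The imaging rules give nearly every subject dosed in Cycle 2 or later a scan, and such a subject enters the EAS through the assessment limb. SAP 7.6 states the intent plainly. Protocol 8.3.1 recognises that unacceptable toxicity can end study participation, 8.3.3 itself speaks of discontinuing due to toxicity, and the current design ends at the EOT visit, so a site might well record toxicity as the reason for leaving the study. The case report form categories are not in the documents. The replacement sentence sits in SAP text that still describes two stages and 34 subjects, whereas the Protocol has limited enrolment to about 20 and no longer mentions replacement.

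Much of this stands. It shows that exclusion is possible rather than demonstrated, and that few subjects would be involved. It does not remove the contradiction between SAP 6.2 and 7.2. Nor does 8.3.1 rescue the literal reading, since it labels those outcomes completion, not discontinuation.

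A reader might go further in three ways that the documents do not support.

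- **That the primary result is biased.** The SAP's primary ORR uses All Treated, which does not depend on EAS membership.
- **That a conclusion could flip.** With 7 responders, dropping 3 subjects moves 7/20 = 35.0% to 7/17 = 41.2%, past the 0.38 design alternative. SAP 7.4.6.6 makes the results descriptive with no formal comparisons, so 0.38 is not a decision boundary here.
- **That replacement inflates the type 1 error.** If 10% of treated subjects were replaced non-responders, a true 0.19 would appear as 0.19/0.90 = 0.211, and the two-stage rule would have a type 1 error of 0.085. With enrolment ended at about 20 and results descriptive, that test will not be run as designed.

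**Conclusion.** The point holds as a definitional inconsistency that should be settled before database lock. SAP 6.2 and 7.2 give opposite answers for a subject who dies before any scan. SAP 7.2 as worded can also omit subjects with toxicity or clinical progression whom 7.6 means to keep. The effect is confined to the EAS response rate, its comparison with All Treated, and the count of about 20.

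The direction is certain: any such exclusion raises the EAS rate, or leaves it at zero. The size is not known. On an assumed 5 responders among 20 treated and 1 to 3 exclusions, the rise is 1.3 to 4.4 percentage points, well inside the 8.7 to 49.1 interval. This rests on the assumed number of subjects who miss both the scheduled and the EOT scan, and on the literal reading of 7.2 being the one programmed.

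**What to change.** **SAP 7.2.** Replace the limb about discontinuing the study with: *whose primary reason for discontinuing study treatment was toxicity or clinical progression, or who died, before any evaluable response assessment*. Add that these subjects count as non-responders. This needs saying, because the default denominator in SAP 7.1.1 is subjects with available data.

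**SAP 6.2.** State that only subjects without a response assessment who stopped for other reasons are non-evaluable and, where replacement still applies, replaced.

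**Protocol 12.1 and 12.3.** Conform both to the same definition. The toxicity-only sentence in the Synopsis, 7.1, 8.3.3 and 10.2.1.1 should then refer to 12.3, so that no new mismatch arises. No change to 8.3.1 is needed.

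**Cost.** Small text changes in both documents, and a possibly slightly lower EAS response rate. No new data are needed: the investigator records a reason for treatment discontinuation (Protocol 8.3.2), the SAP already summarises it (7.3.1), and all deaths go on the case report form (Protocol 10.2.3). One check is worthwhile. Protocol 8.3.2 names confirmed progression, not clinical progression, so confirm that the recorded reasons can identify the latter.

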## 7.3 Study Subjects

### 7.3.1 *Disposition of Subjects*

Subject disposition will be summarized for all enrolled subjects. Summaries will include the number and percentage of subjects in each analysis population, receiving each study drug and both study drugs, study completion, primary reason for early discontinuation of treatment, and primary reason for early discontinuation from study.

### 7.3.2 *Protocol Deviations*

Important protocol deviations will be summarized over all subjects combined for the All Treated Population and will be listed for all subjects. Important protocol deviations are

protocol deviations captured on-study that are deemed by the Sponsor to potentially impact the efficacy or safety conclusions of the study.

All important protocol deviations will be determined and appropriately categorized prior to database lock. Important deviations are collected as “major”. The number and percentage of subjects with any important protocol deviations as well as the number and percentage of subjects with deviations within each category will be presented. Protocol deviations related to the coronavirus (COVID-19) pandemic will be summarized and listed separately.

## **7.4 Efficacy Evaluation**

### **7.4.1 *Datasets Analyzed***

All efficacy summaries will be based on the All Treated Population, as described in [Section 7.2](#). A data listing of subjects excluded from the efficacy analysis, to include the reason for exclusion, will be presented.

### **7.4.2 *Demographic and Other Baseline Characteristics***

Demographic variables including age, sex, ethnicity and race will be summarized for the All Treated Population. Age will be summarized using descriptive statistics. Sex, ethnicity, and race will be summarized with the number and percentage of subjects in each parameter category.

Baseline characteristics include medical history, cancer history, prior cancer treatment, height, weight, body mass index (BMI), smoking history, and ECOG performance status. Disease characteristics include disease stage at study entry, type of staging, site of primary tumor, HPV status, PD-L1 status, time from diagnosis of HNSCC, number of tumors, and sum of target lesion diameters. Height, weight, BMI, time from diagnosis of HNSCC, number of tumors, and sum of target lesion diameters at baseline will be summarized using descriptive statistics; frequency counts and percentages to summarize prior cancer treatment, smoking history, ECOG performance, disease stage, type of staging, site of primary tumor, HPV status, and PD-L1 status at baseline will be presented. Frequency counts and percentages to summarize subjects reporting medical history by body system will also be presented.

### **7.4.3 *Measurements of Treatment Compliance***

Treatment compliance will be summarized for the All Treated Population. The numbers of delays of each study drug will be presented. For Pembrolizumab, which is administered as an infusion, the drug administration could be interrupted or discontinued. For ADU-S100, which is administered as an injection, the drug administration could be paused or stopped. The number and percentage of subjects with delays of each study drug will also be presented.

#### 7.4.4 *Primary Efficacy Endpoint Analysis Methods*

The primary efficacy endpoint is ORR as defined in [Section 6.4.1.1](#) and will be summarized for the All Treated Population.

Summaries of ORR will include the number and percentage of subjects with an objective response and the corresponding two-sided 95% confidence interval (CI) based on the exact binomial method (Clopper-Pearson). Waterfall plots will be provided showing the best overall tumor response. A swimmer plot of disease status for RECIST and iRECIST will be provided. Also, a spider plot of percent change in tumor size relative to baseline will be provided.

Tumor diameters recorded on the Target and New Lesions CRF pages will be utilized for analysis summaries. Diameters recorded on the Dose Administration CRF page or the Injected Lesion Photo CRF page will not be utilized for analysis.

##### 7.4.4.1 *Supplemental Analysis for Primary Efficacy Endpoint*

Of exploratory interest are potential differences in tumor shrinkage in injected target lesions and non-injected target lesions within the same subject. A waterfall plot showing the maximal percentage change from baseline for sum of diameters (SOD) for injected target lesions and for SOD for non-injected target lesions will be provided dependent on collection of measurement data for both types of target lesions. Tumor measurements recorded on Target Lesion and New Lesion pages will be utilized for analysis. Measurements on the Dose Administration page will not be utilized here.

The protocol specifies that if an injected lesion shows signs of significant regression (i.e. shrinkage) that precludes the ability to re-inject the lesion, other accessible lesions may be injected. As such, a non-injected target lesion may become an injected target lesion at a subsequent timepoint. As stated in [Goldmacher et al 2020](#), "... it is not meaningful to report maximal shrinkage of injected lesions compared with the chronologic baseline. ... measuring the maximal effect on only the lesions initially chosen for injection may miss critical information."

Under these considerations, data for the injected target and non-injected target lesions will be analyzed on an exploratory basis using the following definitions adapted from [Goldmacher et al 2020](#):

- A. For injected target lesions, the baseline for each individual lesion will be defined as the measurement obtained prior to first injection of that lesion. Specifically,
  - For target lesions injected at C1D1, the baseline will be defined as the measurement obtained prior to C1D1.
  - As the protocol allows for injection of other accessible lesions if a lesion shows signs of significant regression (i.e. shrinkage) that precludes the ability to re-inject the lesion, the baseline measurement for these newly injected lesions will be the preceding measurement obtained prior to the

lesion's initial injection. The baseline for these lesions will not be the measurement prior to C1D1.

- As this analysis will consider any new lesion target lesions (per iRECIST), if these new target lesions are injected, the baseline measurement for these lesions will be the preceding measurement obtained prior to the lesion's initial injection. The baseline for these lesions will not be the measurement prior to C1D1.
- Baseline SOD is defined as the sum of the individual lesion diameters at baseline. If a lesion becomes injected after C1D1, the baseline injected SOD will incorporate data from different timepoints.
- Best response SOD also can incorporate data from different timepoints, regardless of if a lesion was injected after C1D1. However, only measurements which occur after initial injection can be considered for best response.

